Social Responsiveness Scale (SRS) (Costantino et al., 2003). This 65-item rating scale measures the severity of autism spectrum symptoms as they occur in natural social settings. Completed by a parent or teacher in 15 to 20 minutes, the SRS provides a clear picture of a child's social impairments, assessing social awareness, social information processing, capacity for reciprocal social communication, social anxiety/avoidance, and autistic preoccupations and traits. It is appropriate for use with children from 4 to 18 years of age. Sensitive and reliable across a wide range of symptom severity, the SRS can be used as a screener in clinical or educational settings, an aid to clinical diagnosis, or a measure of response to intervention. SRS scores are particularly helpful in identifying Autism, Asperger's Disorder, Pervasive Developmental Disorder Not Otherwise Specified (PDD-NOS), and Schizoid Personality Disorder of Childhood.

Short Sensory Profile (SP) (Dunn, 1999). The Short Sensory Profile is a 38-item caregiver questionnaire and score sheet designed for use in screening and research protocols. The items on the Short Sensory Profile are grouped into three major sections: sensory processing, modulation, and behavioral and emotional responses. In a recent report it was found that sensory sensitivities were related to sleep difficulties in children with ASD (Hollway, Aman, Butter, 2013). We will use the SP to track sensory sensitivities which may be related to avoidance behavior that interferes with family QOL, over the course of the study. The SP will be an exploratory measure.

Repetitive Behavior Scale – Revised (RBS-R) (Lam & Aman, 2007). The RBS-R is a 43-item self-report questionnaire that is used to measure the breadth of repetitive behavior in children, adolescents, and adults with Autism Spectrum Disorders. The RBS-R provides a quantitative, continuous measure of the full spectrum of repetitive behaviors. The RBS-R consists of six subscales including: Stereotyped Behavior, Self-injurious Behavior, Compulsive Behavior, Routine Behavior, Sameness Behavior, and Restricted Behavior that have no overlap of item content. This permits differential identification and scoring of discrete varieties of repetitive behaviors. Participants are asked to read a list of behaviors and choose a score that best describes how much of a problem the behavior has been. Behaviors are rated on a 4-point scale: 0-Behavior does not occur, 1-Behavior occurs and is a mild problem, 2-Behavior occurs and is a moderate problem, 3-Behavior occurs and is a severe problem. We will use the RBS-R to assess repetitive behaviors and improvement over the course of the study.

Swanson, Nolan, and Pelham Version IV Parent Rating Scale (SNAP-IV). The SNAP-IV ADHD and ODD sections include the 18 DSM-IV symptoms of ADHD (9 hyperactive/impulsive items

and 9 inattention items) and eight symptoms of ODD (Oppositional Defiant Disorder) on a 0-3 metric; it can be downloaded from www.adhd.net. We will use the SNAP-IV to assess ADHD and ODD symptoms and improvement over the course of the study.

Objective Measure of Sleep

Motionlogger Micro Watch (Ambulatory Monitoring). The Motionlogger Micro Watch includes basic sleep estimation with simultaneous environmental data collection. A range of recording capabilities exist including four validated sleep algorithms and a suite of circadian rhythm analyses. The software package allows for quick easy download of actigraph data. Study participants will wear the actigraph on five consecutive nights between the Screen and Baseline Visits, between Visit 5 and 6 and again between visits 9 and 10.

Safety Measures

Laboratory Tests. On three separate occasions during the study participants will have blood drawn and laboratory tests will be conducted to assess any changes in test values since the Screening Visit. Blood and urine will be collected at the Screen Visit, at the Endpoint of the first phase (Week 12), and at the Endpoint of the last phase (Week 28). The following tests will be run on the blood samples: ALT, AST, total and direct bilirubin, creatinine, CRP, IL-6, and CBC. The following tests will be run on the urine samples: standard urinalysis, to evaluate protein, PH, glucose, ketones, nitrites, appearance, color, specific gravity, and bacteria.

Adverse Events (AEs). To minimize the risk, subjects will be systematically monitored. AEs, vital signs, including resting BP, will be evaluated at each visit throughout all phases of the study. When the treating clinician elicits an AE, it will be documented on a case report form, regardless of suspected relationship to the essential oil. For all AEs, the investigator will obtain sufficient information to determine the onset, course, and outcome of the AE. If a subject has experienced an AE, the subject may return to the site for an unscheduled visit at the PI's discretion. If any of these AEs are serious and/or unexpected, the site PI will contact the Sponsor and notify the IRB as appropriate.

Potential AEs include sun sensitivity due to the Bergamot in the essential oil, possibly gynecomastia in pre-pubescent males due to the lavender oil in the essential oil, and skin irritation at the application site.

Sample Characteristics

Demographic Profile. This will be completed by the parent / caregiver at screening to document basic demographic information (parent education, occupation, and marital status).

Cognitive / Developmental Measures. Depending on the age and functioning level of the child, the Stanford-Binet Intelligence Scales; 5th Edition abbreviated battery (Nagle & Bell, 1993) or Mullen Scales of Early Learning AGS Edition will be administered (Mullen, 1995). These are the two cognitive/developmental measures used in the Autism Treatment Network and our other projects. We will evaluate level of cognitive functioning to characterize our sample. The IQ test results will be used to characterize our sample via mean and standard deviation.

Social Validity

Consumer Satisfaction Questionnaire. The Consumer Satisfaction Questionnaire will be filled in by parents at the end of both the first condition and the second. This questionnaire will be used to determine parents level of satisfaction with the study conditions and procedures. The Consumer Satisfaction Questionnaire (CSQ) speaks to feasibility of a larger study, which is one of the study's aims.

Masking Questionnaire. The Making Questionnaire will be completed by parents and by a study clinician at Visit 10 (Week 28). This questionnaire will be used to determine whether parents and clinicians can guess the oils that parents received during the first and last 3 months of the study and why. This questionnaire will provide information about the efficacy of masking essential oils treatments that may be useful for future studies.

Data Analytic Plan

The primary goal of this double-blinded randomized pilot study is to establish the feasibility of a full-scale study by evaluating (1) recruitment (retention and adherence), (2) safety, (3) and preliminary evaluation of the effect on the clinical outcomes. The primary outcome is QOL. Chief secondary outcomes are CSHQ, AAS and PSI. Exploratory outcomes include DD-CGAS, ABC SRS, RBS and Actigraphy.

Data analysis will be primarily comparing Reconnect to the control condition. For dropouts, we will do a terminal evaluation and evaluate whether it is related to study oils or procedures or to some unrelated issue (e.g., moving away), and report the pattern of drop out. If more subjects drop out at a very early stage (week 1 or 2) than expected based on our experience, we will consider recruiting additional subjects to insure 28 subjects experiencing both conditions.

Demographic and recruitment information will be summarized. Frequency tables will be used to summarize toxicity and tolerability based on type, severity, and attribution of the adverse events during each condition. Clinical outcomes will be plotted and summarized for all subjects over time by individual and condition. Data summaries for missing and outlying data will be distributed and reviewed. Visual displays will be generated and presented to investigators in order to identify any outliers or other problems that could be missed by summary statistics. The categorical outcomes will be tabulated for each condition. The effect sizes of the changes of these clinical outcomes after 12 weeks will be estimated, using Cohen's definition, for each condition. Each phase will last for a total of 12 weeks. The effect size of active vs control condition will be calculated as the differences of the mean improvements between conditions, divided by pooled standard deviation of the improvements from the two groups.

Sample size and Randomization

This randomized crossover pilot study will have 28 subjects randomized into 2 orders of condition with a block size of 4 initially, then block size of 2 as the sample size nears

[figure not shown]
completion. Considering up to 15% early drop outs due to reasons not related to essential oils, we plan to randomize up to 33 subjects.

With 28 participants in this crossover study and using the participants as their own controls we estimate that we will be able to detect statistical significance with an effect size of **0.8.** In addition, we will compare the changes of the clinical outcome variables between Reconnect and control conditions by testing the interaction of condition and time based on a linear mixed model for repeated measurement, with conventional alpha of 0.05 for the primary outcome. In order to protect against Type 2 error in this pilot study, we will not correct for multiple tests.

Study Time Line

Study Timeline. The time-line for the study appears in Figure 1. The first several months will be used to obtain IRB approvals and create Case Report Forms or source documents. The next 19 months will be used for participant recruitment, supplementation, and assessment. Finally, the last 3 months will involve data analysis and manuscript writing.

Table 3. Study Timeline (24 months)

REFERENCES

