Our primary aims are to evaluate the feasibility of a larger study and examine preliminary data regarding benefit and tolerability of an essential oil formulation distributed by Young Living Essential Oils, Lehi, UT., for enhancing QOL in children with ASDs. We will develop preliminary data suitable to be submitted in a competitive NIH grant application for a larger multisite study. The proposed study will include a 7-month crossover with two 3-month conditions and a month washout between, with randomly assigned order. The 2 conditions will be a proprietary formula of essential oils and a scented coconut oil comparator. Measures of QOL, equanimity, and sleep health will include parent report on valid and reliable rating scales.

Primary Hypotheses

1. We can recruit 28 participants in 2 years with 85% adherence and 85% retention through both conditions.

- 2. With essential oils, participants will show significantly improved QOL on the Pediatric Quality of Life Inventory compared to the control condition, with a medium effect size.
- 3. While receiving essential oils participants will show negligible or no increases in adverse events (AEs), including allergic contact dermatitis, immediate contact reactions (contact urticaria), and photosensitivity, compared to the control condition.

Secondary Mediational Hypotheses

- 1. With essential oils, compared to the control condition, participants will show significantly improved sleep onset and maintenance on objective and subjective measures (actigraphy; parent sleep diaries, and parent and clinician-rated scales) with a medium effect size, and this will mediate the improvement in QOL.
- 2. With essential oils, compared to the control condition, participants will display greater equanimity and improvements in mood and daytime behavior on objective and subjective measures (heart rate; parent and clinician rated scale) compared to the control condition and this will mediate the improvement in QOL.

Participant Inclusion/Exclusion Criteria

Inclusion Criteria

Entry criteria are the following:

- i. Outpatients between 3 and 9 years of age, inclusive;
- ii. Diagnosis of Autism Spectrum Disorder (ASD) by DSM-V;
- iii. Total item mean score of > 1.5 on PedsQL Inventory;
- vi. Care provider who can reliably bring subject to clinic visits and provide trustworthy ratings.

Exclusion Criteria

Exclusion criteria are the following:

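### The Reconnect-versus-control effect size has no period or order term and the model's time term is undefined, so period drift costs precision and, if completers differ between orders, shifts the effect

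*Combined protocol and SAP*

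**What the plan says.** Specific Aims/Hypotheses describes the design: "The proposed study will include a 7-month crossover with two 3-month conditions and a month washout between, with randomly assigned order". Sample size and Randomization fixes the allocation: "This randomized crossover pilot study will have 28 subjects randomized into 2 orders of condition with a block size of 4 initially", with smaller blocks near the end.

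The Data Analytic Plan gives the effect measure: "The effect size of active vs control condition will be calculated as the differences of the mean improvements between conditions". The divisor is the pooled SD of the improvements. For testing, Sample size and Randomization adds a comparison of changes by "testing the interaction of condition and time based on a linear mixed model for repeated measurement", at alpha 0.05 for the primary outcome. Time is not defined. Period, order and carryover are nowhere named as analysis terms.

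On losses, the Data Analytic Plan will report their pattern and reasons, and would consider extra recruitment if very early dropout is high. The sample-size section adds: "Considering up to 15% early drop outs due to reasons not related to essential oils, we plan to randomize up to 33 subjects". No analysis rule covers unequal loss between the two orders.

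Table 1 schedules PedsQL at Screening, Week 12 and Week 28, and PSI at Weeks 0, 12 and 28. CSHQ and AAS are rated at every visit, including Week 16, the second baseline.

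**The concern.** Randomising the order of conditions lets a crossover separate treatment from the passage of time. A raw difference of condition means does not use that.

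A shift between periods is plausible. The children are 3 to 9 years old, the two endpoints are 16 weeks apart, parents rate repeatedly, and condition 1 has four on-treatment visits (Weeks 2, 4, 8, 12) against three in condition 2 (Weeks 20, 24, 28).

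If the orders stay balanced, the shift adds noise. If completers are unbalanced, part of it becomes apparent benefit or harm. Imbalance need not be random: skin irritation at the application site is a listed potential adverse event, and oil-related loss during condition 1 would fall in the Reconnect-first order. The estimates are meant to support a grant application for a larger trial, and the plan forgoes multiplicity correction to protect against Type 2 error.

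**Working it through.** **1. The plan's own figures.** 28/(1 − 0.15) = 32.9, rounded up to 33, which reproduces. The statement "we estimate that we will be able to detect statistical significance with an effect size of 0.8" cannot be reproduced, because no power, sidedness, SD or within-child correlation is given. With n = 28, two-sided 5%, a paired test has 98% power at 0.8 SD of the within-child difference and 80% power at 0.55. Two independent groups of 28 would have 84% power at 0.8.

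**2. What drift enters.**
- PedsQL and PSI: with both improvements measured from the initial baseline, (Week 12 − baseline) and (Week 28 − baseline), the baseline cancels within child. Week 12 against Week 28 remains, with all drift between them.
- CSHQ and AAS: with improvements over Weeks 0–12 and 16–28, steady drift cancels. Only a difference in change between periods remains.

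**3. Algebra.** Let D be Reconnect minus control within child, τ the true effect, π the period shift (period 2 minus period 1), n1 the Reconnect-first completers, n2 the control-first completers, and n = n1 + n2. Then E[D] = τ − π (Reconnect first) or τ + π (control first).
- Unadjusted mean: τ + π(n2 − n1)/n.
- Equal orders: the SD of D is multiplied by √(1 + π²) when its SD is 1, and the pooled SD of improvements by √(1 + π²/4).
- Period-adjusted estimate: the average of the two order-specific means of D, which is τ whatever π is.

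Assumed, because the documents give none of these: SD of improvement 1, within-child correlation 0.5 (so SD of D = √(2 × 0.5) = 1), no carryover, children with both endpoints analysed, and π = 0.25, 0.5 or 0.75.

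**4. Equal orders, 14/14.** Bias is zero. The paired test shown is one the plan does not specify; power is by simulation.

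| π | Pooled SD × | Effect size 0.5 becomes | SD of D × | Power at 0.5, unadjusted | Power at 0.8, unadjusted |
|---|---|---|---|---|---|
| 0 | 1 | 0.500 | 1 | 72% | 98% |
| 0.25 | 1.008 | 0.496 | 1.03 | 70% | 98% |
| 0.5 | 1.031 | 0.485 | 1.12 | 64% | 97% |
| 0.75 | 1.068 | 0.468 | 1.25 | 53% | 94% |

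With a period term, power stays at 72% and 98% in every row. The unadjusted test is conservative: its type I error is about 3% at π = 0.5.

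**5. Unequal completers.** The retention target is "We can recruit 28 participants in 2 years with 85% adherence and 85% retention through both conditions", and 0.85 × 28 = 23.8, so take 24 completers.
- 14/10 (all four losses in the control-first order): bias = π(10 − 14)/24 = −π/6, or −0.04, −0.08, −0.13. Unadjusted paired power at 0.5 is 55%, 41%, 25%; adjusted power is about 64%, without bias.
- 13/11 (losses split 3/1): bias = −π/12, or −0.02, −0.04, −0.06.
- 12/12: bias zero.
- 17/11 (33 randomised, five lost from one order): bias = −6π/28, or −0.05, −0.11, −0.16.

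The signs reverse if the losses fall in the Reconnect-first order; drift towards improvement would then favour Reconnect.

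**6. How likely is 14/10?** If four of 28 are lost at random, all four fall in one order with probability 2 × 1,001/20,475 = 9.8%, they split 3/1 with 10,192/20,475 = 49.8%, and 2/2 with 8,281/20,475 = 40.4%.

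**The case against.** The best defence is that the test is a mixed model containing time. If time means study week, its main effect would act as a period term, so for the test this is an ambiguity and not a proven omission. That stands. It does not rescue the effect-size formula, which has no such term on either reading. It also raises a question of its own: over the two PedsQL endpoint weeks, a condition-by-week interaction in a two-order crossover is aliased with randomised order and is not the Reconnect effect.

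Second, the power losses belong to an unadjusted paired test that the plan does not state. On the stated formula, balanced drift only shrinks the effect size slightly, and at the plan's own 0.8 even the paired test loses little. This stands too.

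Third, 14/10 is an extreme split, blocking balances entry, and up to 33 will be randomised. Extra recruitment restores numbers, however, not balance between orders among completers.

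Fourth, drift over the 16 weeks does not apply to CSHQ and AAS when each change has its own baseline. That is correct, and the point is limited accordingly.

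**Conclusion.** The point holds for the effect-size formula, most directly for PedsQL and PSI. For the mixed model, the finding is that time must be defined. With equal orders the effect is unbiased and its pooled SD grows by about 1%, 3% or 7% over the assumed drifts. With unequal completers the bias is the drift times (n2 − n1)/n: one sixth of the drift if all four of 28 losses fall in one order, one twelfth for a 3/1 split. Against a standard error of about 0.20 (1/√24), even the 14/10 bias of 0.04 to 0.13 SD is modest.

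A reader might infer that the planned test certainly ignores period, that the trial will report a biased effect, or that false positives rise. The documents do not support this. The test may absorb period, bias needs both drift and unequal completion, and with balanced orders an unadjusted paired test errs towards caution. The sizes rest on assumed drift, SD and correlation. This is a change that should be made because it is almost free, not a flaw that invalidates the pilot.

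**What to change.** In the Data Analytic Plan and in Sample size and Randomization:

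- Estimate the Reconnect-minus-control difference from a mixed model with fixed effects for condition, period (1 or 2) and randomised order, and a random child effect. The period term removes the drift; order alone would not.
- For PedsQL and PSI, use the end-of-condition score as response, with the initial baseline as covariate. The condition contrast replaces the condition-by-time test for these two scales.
- For CSHQ and AAS, define time as weeks within condition and keep the condition-by-time test, adding period and period-by-time terms.
- Derive the effect size from the adjusted condition contrast, and state which SD divides it.

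No new data or visits are needed. The cost is one degree of freedom. At an effect of 0.5 with no drift, paired power falls by about 0.1 point at 14/14 (72.3% to 72.1%), 1.4 points at 14/10 (65.0% to 63.6%) and 2.1 points at 17/11 (72.3% to 70.1%).

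The plan should also say what this does not cover. A period term removes neither carryover nor a condition-by-period interaction, such as families rating the oils differently in period 2 because they have by then smelled both.

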Prunus amygdalus dulcis (Sweet Almond) oil	Protects skin's barrier function and keeps it from drying - used in body lotions, face creams, and body oils; anti- inflammatory and pain relieving	CIR approved as safe for topical application; absorbs slowly through skin; completely digested if taken orally; non-irritating and non-sensitizing in any concentration **Nut/almond allergies	Oleic acid (62-86%), Linoleic acid (20- 30%), other fatty acids, α-tocopheral, arginine, phytosterols, polyphenols	Almond oil (prunus amygdalus dulcis) – the universal skin oil (n.d.). Bio G Cosmetics. Web.
Boswellia sacra oil	"Frankincense." Perfumes and skin care; edible. Potential anti-depressant. Studies suggest it may have cancer- killing properties and improve osteoarthritis.	Not CIR or FDA approved, but widely used and appears to be well tolerated	Acid resin (56%), gum (similar to gum arabica) (30-36%), 3- acetyl-β-boswellic acid, α-boswellic acid, incensole acetate, phellandrene	Martin, N. (n.d.). Sacred Frankincense Essential Oil - The Original Oil Given to Baby Jesus? Experience-Essential-Oils.com. Web.
Citrus aurantium bergamia peel oil	Helps with heartburn, gas, insomnia, mild depression, and upset stomach (Martin).	FDA approved as a Food Additive and generally regarded as safe, but not recommended for children < 5 years old and can result in skin irritation, particularly from frequent usage or UV light exposure (Martin).	α-pinene, myrcene, limonene, α- bergaptene, β- bisabolene, linalool, linalyl acetate, nerol, neryl acetate, geraniol, geraniol acetate and α- terpineol (Bergamot)	Bergamot essential oil information (2014). Esoteric Oils CC. Web. Martin, N. (n.d.). The Benefits of Bergamot include Easing Stress from Mind & Body! Experience-Essential-Oils.com. Web.
Commiphora myrrha oil	Helps clear colds, bronchitis, cough by removing mucus; used for chapped skin, eczema, skin ulcers, ringworm, skin wounds	Non-toxic, non-irritating, and non-sensitizing	α-pinene, cadinene, limonene, cuminaldehyde, eugenol, m-cresol, heerabolene, acetic acid, formic acid	Myrrh essential oil information (2014). Esoteric Oils CC . Web.

Lavandula angustifolia oil	Natural antibiotic, anti-depressant, sedative; promotes healing and stimulates the immune system (Worwood 1990); Pain relief, antiseptic, stress and anxiety relief, burns and insect bites, aromatherapy ("Lavender Oil").	Topical application can sometimes cause irritation; likely safe in food and possible safe in medicinal amounts; disrupts hormones in prepubertal boys and can result in gynecomastia (abnormal breast growth) (Henley 2007)	Linalool (51%) and linalyl acetate (35%) mostly. Other components include α-pinene, limonene, 1,8-cineole, cis- and trans-ocimene, 3- octanone, camphor, caryophyllene, terpinen-4-ol and lavendulyl acetate ("Lavender Oil")	Henley, D.V. (2007) Prepubertal Gynecomastia Linked to Lavender and Tea Tree Oils. N Engl J Med. 356(5), 479-485. "Lavender Oil." Wikipedia. Wikimedia Foundation (2014). Web. Worwood, V.A (1990) The Fragrant Pharmacy. London: Macmillan.
Pelargonium graveolens flower oil	Antidepressant, anxiolytic, astringent, diuretic	Generally regarded as safe and approved as a food additive by the FDA; non-toxic, non-irritant and generally non-sensitizing	α-pinene, myrcene, limonene, menthone, linalool, geranyl acetate, citronellol, geraniol and geranyl butyrate	Rose geranium essential oil information (2014). Esoteric Oil CC . Web.
Callitris intratropica wood oil	Fragrances; helps with arthritis and asthma	No contraindications found; generally regarded as safe	Guaiol, guaienes, selinenes, guaiazulene, eudesmols, furnanones	Rose, Jeanne. 375 Essential Oils and Hydrosols. Berkeley, CA: Frog, 1999. 51. Blue Cypress Essential Oil. AromaWeb. Web.
Cananga odorata flower oil	Antidepressant, aphrodisiac, hypotensive, sedative; helps with oily skin, anxiety, tension, and fear	Non-toxic, non-irritating, and in most cases non-sensitizing, but sensitivity has been reported and headaches and nausea can result from excessive use.	Linalool, geranyl acetate, caryophyllene, p-cresyl methyl ether, methyl benzoate, benzyl acetate, benzyl benzoate and other sesquiterpenes.	Ylang-ylang essential oil information (2014). Esoteric Oil CC . Web.
Aniba rosaeodora wood oil	Anti-depressant, mildly analgesic, antiseptic, aphrodisiac; helps with headaches	Non-toxic, non-irritating, non-sensitizing; generally regarded as safe	α-pinene, camphene, geraniol, neral, geranial, myrcene, limonene, 1,8-cineole, linalool, benzaldehyde, linalool oxides and a-	Rosewood essential oil information (2014). Esoteric Oil CC . Web.

			terpineol	
Picea mariana (Spruce) leaf oil	Helps with arthritis, infections, and pain; supports the immune system	FDA approved Food Additive and Flavoring Agent; non-toxic and generally safe but could result in skin irritation	Pinenes, limonene, boryl acetate, tricyclene, phellandrene, thujone	Martin, N. (n.d.). Spruce Essential Oil offers Support for Muscles and the Immune System! Experience- Essential-Oils.com. Web.
Hyssopus officinalis leaf oil	Used in cooking; medicinally used as a cough suppressant and expectorant; helps with nervous exhaustion and grief	Contains thujone which stimulates the CNS and can cause seizures as the oil, even in low doses, in children; otherwise non-irritating and non-sensitizing	α-pinene, camphene, β-pinene, sabinene, myrcene, limonene, pinocamphone, isopinocamphene, γ- terpineol, 1,8-cineole and thujone	Woolf, A. (1999). Essential Oil Poisoning. Clinical Toxicology , 37(6), 721-727.
Rosa damascena flower oil	Helps with dry skin/eczema, asthma, heart arrhythmia, high BP; anti- depressant, sedative, laxative, aphrodisiac, anxiolytic	Non-toxic, non-irritating, and non-sensitizing	300+ compounds, but main ones are citronellol, phenyl ethanol, geraniol, nerol, farnesol, stearpoten, α-pinene, myrcene, limonene, menthone, and linalool (Rose)	Woolf, A. (1999). Essential Oil Poisoning. Clinical Toxicology, 37(6), 721-727. Rose geranium essential oil information (2014). Esoteric Oils CC. Web.
Santalum paniculatum (Royal Hawaiian Sandalwood) wood oil	Perfume, meditation, relaxation; Helps chapped skin, scars, and stretch marks; anti-inflammatory, a disinfectant, diuretic, and anti-depressant; said to help with insomnia, bug bites, headaches, depression	May cause skin irritation and should be diluted.	100% steam-distilled pure Sandalwood oil from Hawaiian trees (organic compounds not specified)	"Royal Hawaiian Sandalwood Essential Oil Santalum Paniculatum." Hana Naia Aromatherapy . Hana Naia LLC, 2014. Web.
Caprylic/capric triglycerides	Ester derived from Coconut oil; Good solvent and emollient, acts as a	Skin exposure shows very low toxicity and no potential for skin/eye irritation/sensitization; FDA approved as a food additive and CIR approved for cosmetic use	Derived from coconut oil and glycerin	"Caprylic/Capric Triglycerides." Truth in Aging . Truthinaging.com, 2013. Web.

	carrier for fat-soluble vitamins; used in cosmetics: hair products, dyes, sunscreen, deodorants, make-up			
Cedrus atlantica (Cedarwood) wood oil	Acne, arthritis, coughing, dermatitis, bronchitis, stress	No special precautions indicated	Atlantone, caryophyllene, cedrol, cadinene	"Atlas Cedarwood Essential Oil." AromaWeb . AromaWeb, LLC, 2014. Web.
Melissa officinalis leaf oil	Antidepressant, sedative, antispasmodic, hypotensive; helps with nausea, headaches	Non-toxic, but could be irritating or sensitizing so should be diluted and not used on sensitive skin	Tannins, eugenol, terpenes, citronellal, octyl benzoate, linalool, nerol, etc	"Melissa Essential Oil (a.k.a. Lemon Balm Essential Oil) Information." Esoteric Oils . Esoteric Oils CC, 2014. Web.
Picea pungens (Idaho blue spruce) branch/leaf/wood oil	Relax the mind and muscles, relieve muscle tension, cleanse minor skin irritations	FDA approved as a Food Additive, so generally safe	45-55% monoterpenes (mostly α-pinene and limonene); 3-12% sesquiterpenes	"Idaho Blue Spruce Essential Oil." Aromatherapy Living with Young Living Essential Oils. Young Living Essential Oils, 2012. Web.

Table 3. Ingredients of coconut oil scented with 0.5% vanilla absolute oil, their uses/actions, and potential side effects.

Scented Coconut Oil	Uses	Safety	Chemical Composition	Citations
Ingredient				
Vanilla Absolute Oil	Found in Madagascar. Used primarily as a fragrance.	A solution of 10% vanillin diluted in petrolatum resulted in occasional contact allergy. In a study by Hausen, no positive reactions to vanillin were found.	Primary constituents include vanillin, vanillic acid, and phydroxybenzaldehyde	"Certificate of Analysis: Vanilla Absolute." Eden Botanicals . Eden Botanicals, 2015. Web. Wöhrl, S., Hemmer, W., Focke, M., Götz, M. and Jarisch, R. (2001), The significance of fragrance mix, balsam of Peru,

				colophony and propolis as screening tools in the detection of fragrance allergy. British Journal of Dermatology, 145: 268–273. doi: 10.1046/j.1365-2133.2001.04345.x Hausen BM. Contact allergy to balsam of Peru. II. Patch test results in 102 patients with selected balsam of Peru constituents. Am J Contact Dermat. 2001;12(2):93–102. [PubMed]
Coconut Oil	Used as a flavoring in foods. Added to some pharmaceuticals and cosmetics. Commonly rubbed on the skin.	Populations of people that consume large quantities of coconut oil show no adverse effects. According to the FDA, "There is no evidence in the available information on coconut oil, peanut oil, and oleic acid that demonstrates, or suggests reasonable grounds to suspect, a hazard to the public as they are now used in paper and cotton packaging material for food at levels now current or as they might reasonably be expected to be used for such purposes in the future."	Composed of 92% saturated fatty oils.	Thampan, P.K., Glimpses of coconut industry in India, Coconut Development Board, Cochin 1988. Krishna, G., Rah, G., Bhatnagar, A. S., Kumar, P., & Chandrashekar, P. Indian Coconut Journal. "Coconut Oil: Chemistry, Production and Its Applications - A Review." 2010. "Select Committee on GRAS Substances (SCOGS) Opinion: Coconut Oil (packaging)." U.S. Food and Drug Administration, Apr. 2013. Web. 02 Jan. 2015.

Human Subjects considerations

Participants:

Participants are 28 children age 3-9 with autism spectrum disorder and excessive anxiety and sleep disturbance. Although we are not treating autism, this population is especially prone to impaired QOL due to sleep problems and anxiety, and is the population for which OTC essential oils are most often used by consumers without adequate test of benefits and safety. Careful evaluation of this practice has been requested by parents of children with autism.

Risks:

Essential oils themselves are generally regarded as safe and are routinely used by the public. One of the purposes of this pilot study is to check whether this assumption is valid. The main known risk/discomfort is from the blood draws, with possible bleeding, bruising, or infection. The ratings pose some time/effort burden for parents and the usual confidentiality risks apply. Although uncommon, skin irritation with topical administration or breast enlargement in boys is a potential side effect of a few ingredients of Reconnect (See Table 2).

Minimization of risk:

Numbing cream will be offered for blood draws, which will be done by experienced phlebotomists. The usual security for personal health information will be used, with locked files accessible only to CITI-trained and HIPAA-trained research staff and password-protected electronic data. Time/effort burden will be partially compensated by payment. All families will be given phone numbers of the PIs and coordinator to reach in the event of some unexpected adverse event. Potential skin sensitivity and potential male breast enlargement will be checked for at each visit by a physician, who may discontinue the oils or switch mode of administration based on clinical judgment.

Ethnic & Sex Composition of sample:

The sample is expected to reflect the ethnic proportions of central Ohio. Sex ratio is expected to mirror that of the autism population, 4:1 boys. Both males and females will be included in the study.
